### **Durable response rate (BICR) in CPS $\geq$ 5 and all randomized subjects**

Durable response will be evaluated per BICR assessment and per investigator assessment for subjects with measurable disease at baseline. The durable response rate will be computed in each treatment group along with the exact 95% CI using Clopper-Pearson method. An estimate of the difference in DRRs and corresponding 95% CI will be calculated using CMH methodology and adjusted by the stratification factors as specified in [Table 7.5-1](#). The stratified odds ratios (Mantel-Haenszel estimator) between the treatments will be provided along with the 95% CI.

### **PFS and ORR as assessed by either BICR or investigator and OS across TPS cut-offs**

See [Section 7.8](#) for Biomarker Analysis.

### **PFS2 in CPS $\geq$ 5 and in all randomized subjects**

PFS2 will be analyzed similarly to PFS:

- Median values based on KM method, along with two-sided 95% CI using Brookmeyer and Crowley method will be calculated. The estimate of standard error will be calculated using the Greenwood formula;
- PFS2 will be graphically displayed along with the median and 95% CI.

A by-subject listing of PFS and PFS2 will be provided.

### **TTSD in CPS $\geq$ 10, 5, 1 and all randomized**

See [Section 7.9.1](#) in Clinical Outcome Assessment.

## **7.6 Safety**

Analyses in this section will be tabulated for all treated subjects by treatment group as treated, unless otherwise specified. In addition some safety selected outputs will be presented for treated CPS  $\geq$  5 Subjects.

For chemotherapy (FOLFOX or XELOX) the Chemotherapy regimen “as treated” will be reported (see [Section 6.2](#)).

### **7.6.1 Deaths**

Deaths will be summarized by treatment group:

- All deaths, reasons for death.
- Deaths within 30 days of last dose received, reasons for death. This output will also be presented for CPS  $\geq$  5 treated subjects.
- Deaths within 100 days of last dose received, reasons for death.

A by-subject listing of deaths will be provided for the all enrolled subjects population.

### **7.6.2 Serious Adverse Events**

Serious adverse events will be summarized by treatment group:

- Overall summary of SAEs by worst CTC grade (any grade, grade 3-4, grade 5) presented by SOC/PT. This output will also be presented for CPS  $\geq 5$  treated subjects.
- Overall summary of drug-related SAEs by worst CTC grade (any grade, grade 3-4, grade 5) presented by SOC/PT. This output will also be presented for CPS  $\geq 5$  treated subjects.

All analyses will be conducted using the 30-day safety window.

A by-subject SAE listing will be provided for the “enrolled subjects” population.

### **7.6.3 Adverse Events Leading to Discontinuation of Study Therapy**

AEs leading to discontinuation will be summarized by treatment group:

- Overall summary of AEs leading to discontinuation by worst CTC grade (any grade, grade 3-4, grade 5) presented by SOC/PT. This output will also be presented for CPS  $\geq 5$  treated subjects.
- Overall summary of drug-related AEs leading to discontinuation by worst CTC grade (any grade, grade 3-4, grade 5) presented by SOC/PT. This output will also be presented for CPS  $\geq 5$  treated subjects.

The analyses will be conducted using the 30-day safety window.

A by-subject AEs leading to discontinuation listing will be provided.

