1.4.2 Summary of Clinical Pharmacology

1.4.2.1 Nivolumab

The PK of nivolumab were studied in subjects over a dose range of 0.1 to 10 mg/kg administered as a single dose or as multiple doses of nivolumab every 2 or 3 weeks. The geometric mean (% CV%) clearance (CL) was 9.5 mL/h (49.7%), geometric mean volume of distribution at steady state (Vss) was 8.0 L (30.4%), and geometric mean elimination half-life (t1/2) was 26.7 days

(101%). Steady-state concentrations of nivolumab were reached by 12 weeks when administered at 3 mg/kg Q2W, and systemic accumulation was approximately 3-fold. The exposure to nivolumab increased dose proportionally over the dose range of 0.1 to 10 mg/kg administered every 2 weeks.

The clearance of nivolumab increased with increasing body weight. The PPK analysis suggested that the following factors had no clinically important effect on the CL of nivolumab: age (29 to 87 years), gender, race, baseline LDH, PD-L1. Although ECOG status, baseline glomerular filtration rate (GFR), albumin and body weight had an effect on nivolumab CL, the effect was not clinically meaningful. When nivolumab is administered in combination with ipilimumab, the CL of nivolumab was increased by 24%, whereas there was no effect on the CL of ipilimumab. Additionally, PPK and exposure response analyses have been performed to support use of 240 mg Q2W dosing in addition to the 3 mg/kg Q2W regimen. Using the PPK model, exposure of nivolumab at 240 mg flat dose was identical to a dose of 3 mg/kg for subjects weighing 80 kg, which was the approximate median body weight in nivolumab clinical trials (see Section 1.1.4). Additional details are provided in the nivolumab investigator brochure (IB). 86

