 - Grade 4 drug-related endocrinopathy AEs, such as hyper- or hypothyroidism, or glucose intolerance, which resolve or are adequately controlled with physiologic hormone replacement (corticosteroids, thyroid hormones) or glucose-controlling agents, respectively, may not require discontinuation after discussion with and approval from the BMS Medical Monitor.
- Any event that leads to delay in dosing lasting > 6 weeks from the previous dose requires discontinuation, with the following exceptions:

Revised Protocol No.: 09 Date: 16-Sep-2019 CA209649

nivolumab

- Dosing delays to allow for prolonged steroid tapers to manage drug-related AEs are allowed.
- Dosing delays lasting > 6 weeks from the previous dose that occur for non-drug-related reasons may be allowed if approved by the BMS medical monitor.
- Any AE, laboratory abnormality, or intercurrent illness which, in the judgment of the Investigator, presents a substantial clinical risk to the subject with continued nivolumab dosing.

Prior to re-initiating treatment in a subject with a dosing delay lasting > 6 weeks from the previous dose, the BMS medical monitor must be consulted. Tumor assessments should continue as per protocol even if dosing is delayed.

The assessment for discontinuation of ipilimumab should be made separately from the assessment made for discontinuation of nivolumab. Although there is overlap among the discontinuation criteria, if discontinuation criteria are met for ipilimumab but not for nivolumab, treatment with nivolumab may continue if ipilimumab is discontinued.

If a subject meets the criteria for discontinuation of ipilimumab but not nivolumab, treatment with nivolumab may not resume until the AE has fully resolved and the subject has discontinued steroids, if they were required for treatment of the AE. The relationship to ipilimumab should be well documented in the source documents. Nivolumab should be resumed at 240 mg every 2 weeks.

If a subject in any of the nivolumab/ipilimumab combination arms meets criteria for discontinuation and investigator is unable to determine whether the event is related to both or one study drug, the subject should discontinue both nivolumab and ipilimumab and be taken off the treatment phase of the study.

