Dispense Study Treatment	X	X	X	First dose to be administered within 3 calendar days after randomization. See Table 4.5.1.1-1. Cycles 2 - 4: subsequent nivolumab and ipilimumab dose may be administered within 3 days before or after the scheduled date if necessary. Subjects may be dosed no less than 18 days between doses. Cycle 5 till EOT: nivolumab 240 mg may be administered up to 2 days before or 3 days after the scheduled date if necessary. Subjects may be dosed no less than 12 days between doses. Nivolumab 480 mg should be given 2 weeks following the last administration of nivolumab 240 mg. Nivolumab 480 mg may be administered up to 3 days before or 3 days after the scheduled date, if necessary. Subjects may be dosed no less than 25 days between doses. Vials may be assigned through IRT up to 3 calendar days prior to every dose date.

^a For subjects receiving nivolumab 480 mg Q4W alone, schedule of study procedures will be aligned with dosing visits (every 4 weeks on Day 1). Laboratory test should be done prior each dose. TSH (with reflexive Free T4 and Free T3; Total T3/T4 are acceptable if Free T3/T4 are not available) is acceptable to perform at alternative dose.

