6.1.1 Serious Adverse Event Collection and Reporting

Section 5.6.1 in the nivolumab and ipilimumab IBs presents the Reference Safety Information to determine expectedness of serious adverse events for expedited reporting. Following the subject's written consent to participate in the study, information on all SAEs, whether related or not related to study drug, must be collected, including those thought to be associated with protocol-specified procedures. All SAEs must be collected from the time of signing the consent, including those thought to be associated with protocol-specified procedures and within 100 days of discontinuation of dosing. For subjects randomized/assigned to treatment and never treated with study drug, SAE information should be collected for 30 days from the date of randomization.

The investigator must report any SAE that occurs after these time periods and that is believed to be related to study drug or protocol-specified procedure.

An SAE report must be completed for any event where doubt exists regarding its seriousness.

If the investigator believes that an SAE is not related to study drug, but is potentially related to the conditions of the study (such as withdrawal of previous therapy or a complication of a study procedure), the relationship must be specified in the narrative section of the SAE Report Form.

SAEs, whether related or not related to study drug, and pregnancies must be reported to BMS (or designee) within 24 hours of awareness of the event. SAEs must be recorded on the SAE Report Form; pregnancies on a Pregnancy Surveillance Form (electronic or paper forms). The required method for SAE data reporting collection is through the eCRF. The paper SAE/pregnancy surveillance forms are only intended as a back-up option when the eCRF system is not functioning. When paper forms are used, the original paper forms are to remain on site. In this case, the paper forms are to be transmitted via email or confirmed facsimile (fax) transmission to:

SAE Email Address: Refer to Contact Information list.

SAE Facsimile Number: Refer to Contact Information list.

For studies capturing SAEs through electronic data capture (EDC), electronic submission is the required method for reporting. In the event the electronic system is unavailable for transmission, paper forms must be used and submitted immediately. When paper forms are used, the original paper forms are to remain on site.

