  - On-treatment AEs will be defined as AEs with an onset date and time on or after the date and time of the first dose of study treatment (or with an onset date on or after the day of first dose of study treatment if time is not collected or is missing). For subjects who are off study treatment, AEs will be included if event occurred within a safety window of 30 days (or 100 days depending on the analysis) after the last dose of study treatment. No “subtracting rule” will be applied when an AE occurs both pre-treatment and post-treatment with the same preferred term and grade.
  - On-treatment evaluations (laboratory tests and vital signs) will be defined as evaluations taken after the day (and time, if collected and not missing) of first dose of study treatment. For subjects who are off study treatment, evaluations should be within a safety window of 30 days (or 100 days depending on the analysis) after the last dose of study treatment.

Late-emergent drug-related AEs will be defined as drug-related AEs with an onset date greater than 100 days after the last dose of study treatment in subjects who are off study treatment.

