#### **7.6.7 Immune-Mediated Adverse Events**

IMAEs will be summarized by treatment group for each immune-mediated category / PT using the 100-day safety window:

- Overall summary of non-endocrine IMAEs by worst CTC grade (any grade, grade 3-4, grade 5) where immune modulating medication was initiated presented by Category / PT. This output will also be presented for CPS  $\geq 5$  treated subjects.
- Overall summary of endocrine IMAEs by worst CTC grade (any grade, grade 3-4, grade 5) presented by Category / PT. This output will also be presented for CPS  $\geq 5$  treated subjects.

- Overall summary of non-endocrine IMAEs leading to discontinuation by worst CTC grade (any grade, grade 3-4, grade 5) where immune modulating medication was initiated presented by Category / PT. This output will also be presented for CPS  $\geq$  5 treated subjects.
- Overall summary of endocrine IMAEs leading to discontinuation by worst CTC grade (any grade, grade 3-4, grade 5) presented by Category / PT. This output will also be presented for CPS  $\geq$  5 treated subjects.
- Overall summary of non-endocrine IMAEs leading to dose delay or reduction by worst CTC grade (any grade, grade 3-4, grade 5) where immune modulating medication was initiated presented by Category / PT. This output will also be presented for CPS  $\geq$  5 treated subjects.
- Overall summary of endocrine IMAEs leading to dose delay or reduction by worst CTC grade (any grade, grade 3-4, grade 5) presented by Category / PT. This output will also be presented for CPS  $\geq$  5 treated subjects.
- Summaries of time-to onset and time-to resolution of non-endocrine IMAEs where immune modulating medication was initiated presented by Category. This output will also be presented for CPS  $\geq$  5 treated subjects.
- Summaries of time-to onset and time-to resolution of endocrine IMAEs presented by Category. This output will also be presented for CPS  $\geq$  5 treated subjects.

A by-subject listing of IMAEs will be provided. By-subject listings of time-to resolution for longest IMAEs cluster (any grade and grade 3-5 in separate summaries) will also be provided. For new studies which collect investigator assessment of potential IMAE data, a by-subject listing of AEs considered as immune-mediated events per investigator but not qualified for IMAEs definition will also be provided.

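### The SAE tables and the overall table of AEs leading to discontinuation stop at 30 days after the last dose, so later-onset events that the trial collects are missing from them

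*SAP*

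**What the plan says.** **The window.** SAP 6.1 defines how it works: "For subjects who are off study treatment, AEs will be included if event occurred within a safety window of 30 days" of the last dose, or 100 days where an analysis says so. It is a rule about when the event occurred, and it applies only to subjects who have stopped treatment.

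**Which tables use 30 days.** For SAEs and drug-related SAEs, SAP 7.6.2 states: "All analyses will be conducted using the 30-day safety window". SAP 7.6.3 has the same rule for all-cause and drug-related AEs leading to discontinuation: "The analyses will be conducted using the 30-day safety window". Neither section repeats its tables at 100 days. Both promise a by-subject listing.

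**How a discontinuation AE is defined.** SAP 7.1.1 identifies it by the action recorded for study drug. Timing is not part of the definition.

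**What the protocol allows and collects.** Section 4.5.1.5 permits up to 6 weeks from the previous nivolumab or ipilimumab dose and then lists exceptions, among them: "Dosing delays to allow for prolonged steroid tapers to manage drug-related AEs are allowed". Delays for non-drug-related reasons may also run longer with medical monitor approval. Table 5.1-2 gives the Q4W visit window: "Nivolumab 480 mg may be administered up to 3 days before or 3 days after the scheduled date, if necessary". SAEs are collected from consent and "within 100 days of discontinuation of dosing" (section 6.1.1), and non-serious AEs for at least 100 days (section 6.2.1).

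**Where the SAP already uses 100 days.** Section 7.6.7 says: "IMAEs will be summarized by treatment group for each immune-mediated category / PT using the 100-day safety window". Those tables include immune-mediated AEs (IMAEs) leading to discontinuation. Deaths (7.6.1), other events of special interest (OEOSI, 7.6.8) and one drug-related AE table (7.6.5) are also shown to 100 days.

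**The concern.** The 30-day limit is shorter than the dosing gaps that the trial permits. A subject can be between doses, with treatment still expected to resume, on day 35. If a new AE then starts and treatment is stopped for it, the AE meets the SAP's definition of an AE leading to discontinuation. Its onset is nevertheless more than 30 days after what has become the last dose, so the table built for such events excludes it. Had the subject resumed dosing, the same AE would have been counted. The exclusion thus depends on the event having ended treatment.

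For SAEs the issue is simpler. The sites collect 100 days of events and the SAE tables use 30 of them.

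Counts of SAEs and of AE discontinuations by arm are among the main safety results. A reader of these tables would take them as complete for the safety follow-up period, and they are not.

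**Working it through.** No planned figure is at issue, so there is nothing of the plan's own to reproduce. The check is day arithmetic and a trace of cases through the rules. Days are counted from the last dose.

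**Inputs**
- Table window: 30 days (SAP 7.6.2, 7.6.3), applied to onset in subjects off treatment (SAP 6.1).
- Permitted gap: 6 weeks = 42 days from the previous dose (protocol 4.5.1.5; SAP Table 7.4.2.1-1 also gives 42 days for nivolumab and ipilimumab), with exceptions beyond that.
- Scheduled nivolumab intervals: 14, 21 and 28 days, each with a late margin of 3 days (protocol Tables 5.1-2 and 5.1-3).
- Collection period: 100 days (protocol 6.1.1, 6.2.1).

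**Step 1: uncovered part of a permitted gap.** 42 − 30 = 12 days (days 31 to 42), which is 12/42 = 29% of the gap. As a share of the time from the due dose to day 42, (42 − 30)/(42 − due day):

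| Schedule | Dose due | Latest in-window dose | Due dose to day 42 | Beyond day 30 |
|---|---|---|---|---|
| Q2W | 14 | 14 + 3 = 17 | 28 days | 12/28 = 43% |
| Q3W | 21 | 21 + 3 = 24 | 21 days | 12/21 = 57% |
| Q4W | 28 | 28 + 3 = 31 | 14 days | 12/14 = 86% |

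On Q4W the latest in-window dose, day 31, already lies past the 30-day limit without any delay.

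**Step 2: uncovered part of the collection period.** 100 − 30 = 70 of 100 days.

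**Step 3: trace three cases** (the days are chosen for illustration).
- *AE starts on day 20, the dose is held, treatment is stopped on day 40.* Onset is within 30 days, so the AE is counted. The date of the decision to stop does not matter.
- *New AE starts on day 35, dosing resumes on day 40.* The AE now precedes the last dose, so it is counted.
- *New AE starts on day 35, treatment is stopped for it.* Onset is 35 > 30 days after the last dose. The AE is not in the 7.6.3 tables and, if serious, not in the 7.6.2 tables.

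**Step 4: where the third case can still appear.**
- As an IMAE: the 100-day tables of 7.6.7, including the one for discontinuation.
- If drug-related: the 100-day table of 7.6.5, but not marked as serious or as the cause of discontinuation.
- If an OEOSI: 7.6.8. If fatal within 100 days: 7.6.1.
- Otherwise: the by-subject listings.

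Two things therefore have no summary table: AEs leading to discontinuation that are not IMAEs and start after day 30, and SAE rates by arm, identified as serious, for days 31 to 100.

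**The case against.** **The window is a deliberate choice.** SAP 6.1 provides for 30 or 100 days by analysis. The shorter one limits events that follow subsequent therapy. This stands as a reason to keep the 30-day tables, not as a reason to have no others.

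**A reader might infer that any event ending treatment during a delay is lost.** It is not. An AE that causes a delay normally starts before the missed dose, by about day 14, 21 or 28, and is counted. Only a new onset after day 30 in a subject who never resumes is affected. A Q4W dose given on day 31 loses nothing by itself, because that subject is still on treatment. In the nivolumab-plus-chemotherapy arm the clock runs from the last dose of any study treatment, so continued chemotherapy extends coverage.

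**A reader might infer that days 31 to 100 survive only in listings.** They do not, as step 4 shows. A late immune-mediated hepatitis treated with immune-modulating medication would be in the 100-day tables of 7.6.7 and, if drug-related, in that of 7.6.5.

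**A reader might infer that the rule flatters the nivolumab arms.** The protocol reports that the "geometric mean elimination half-life (t1/2) was 26.7 days", so about 0.5^(30/26.7) = 46% would remain at day 30 under simple exponential decay. That is a share of drug, not of events. Long gaps are not confined to nivolumab: a chemotherapy component may be delayed 6 weeks, or longer if the investigator sees benefit (protocol 4.6.2.1, 4.7), and SAP Table 7.4.2.1-1 sets no maximum for chemotherapy. Q4W dosing came only with Amendment 29, after accrual ended, and in the nivolumab-plus-chemotherapy arm it needs all chemotherapy stopped and at least 6 months on study. The direction of any bias is unproven.

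**A reader might treat differences between the 7.6.3, 7.6.7 and disposition counts as errors.** They measure different things: all AEs by recorded action, a restricted immune-mediated subset, and the reason on the subject-status CRF page. Disagreement alone would not show a fault.

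**Dose delays and reductions (7.6.4)** also use 30 days, but a delay followed by resumed dosing precedes the last dose and is counted, so little is lost there.

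**Conclusion.** The point holds in a limited form. The overall discontinuation table omits AEs that meet the SAP's own definition but start more than 30 days after the last dose, and the SAE tables omit SAEs on days 31 to 100. In time, that is 12 of the 42 days of a permitted gap, more where a steroid taper or an approved reason extends it, and 70 of the 100 days of collection.

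These are shares of time, not of events. The documents give no event rates by time since last dose, so neither the number of subjects nor the effect on any comparison of arms can be stated. The loss is mainly of discontinuation AEs that are not IMAEs and of by-arm rates of events identified as serious.

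The conclusion rests on reading SAP 6.1 as written, with the window applied to onset, and on counting the 42 days from the previous dose as protocol 4.5.1.5 does. It is a worthwhile improvement to the safety tables. It does not show that the planned safety results are biased towards any arm.

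**What to change.** - **SAP 7.6.3:** count every AE whose recorded action is discontinuation, regardless of days since the last dose; or repeat both tables with the 100-day window, as 7.6.7 does for IMAEs.
- **SAP 7.6.2:** repeat the SAE and drug-related SAE tables with the 100-day window and place them beside the 30-day ones, as 7.6.5 does for drug-related AEs.
- **Keep the 30-day tables.** SAP version 5.0 followed the clinical study report for nivolumab plus chemotherapy, and the 30-day versions are needed for comparison with it.

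The cost is SAP wording and a re-run of existing programs on data already collected. The drawback is that the 100-day tables may include some events that occur after subsequent therapy; a footnote should say so.

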### **7.6.4 Adverse Events Leading to Dose Modification**

AEs leading to dose delay/reduction will be summarized by treatment group:

- Overall summary of AEs leading to dose delay/reduction by worst CTC grade (any grade, grade 3-4, grade 5) presented by SOC/PT.
- Overall summary of related AEs leading to dose delay/reduction by worst CTC grade (any grade, grade 3-4, grade 5) presented by SOC/PT.

The analysis will be conducted using the 30-day safety window.

A by-subject AEs leading to dose delay/reduction listing will be provided.

